8.4.2 Serious Adverse Events (SAEs) and Unanticipated Problems (UPs)

A serious adverse event (SAE) is an AE that, in the view of *the investigator or sponsor*, results in any of the following outcomes:

1. Death
2. Life-threatening event

-
- The decision is based on the investigator's opinion. Must place the subject at immediate risk of death. Example: Anaphylaxis. An adverse event that, had it occurred in a more severe form, might have caused death
3. An event requiring inpatient hospitalization or prolongation of existing hospitalization. This excludes any planned hospitalizations for elective procedures that are not related to study participation.
 4. A persistent or significant incapacity or substantial disruption of the ability to conduct normal life functions
 5. A congenital anomaly/birth defect subsequent to the administration of the agent
 6. An important medical event that may not result in death, be life-threatening, or require hospitalization, but may be considered serious that, based upon appropriate medical judgment, may jeopardize the patient or subject and may require medical or surgical intervention to prevent one of the outcomes listed above

Note on inpatient hospitalization and prolongation of hospitalization: Subject must be hospitalized for more than 24 hours. Going to the hospital for observation does not meet the definition of hospitalization. Emergency room visits that do not result in an admission to the hospital should be evaluated for one of the other serious outcomes (e.g. life-threatening, required intervention to prevent permanent damage; other serious medically important event).

All related SAEs occurring at any time during the 2-year treatment and additional year of follow-up will be reported to NIDCR via the CROMS contractor, as well as to COMIRB and NNHRRB within 72 hours of receipt of information about the SAE. All SAEs will be recorded on the appropriate SAE CRF, be followed through to resolution or stabilization by a study clinician, and be reviewed and evaluated by a study clinician.

An unanticipated problem involving risks to the subjects or to others (UP). This would be any incident, experience, or outcome that meets all of the following criteria:

1. Unexpected (in terms of nature, severity, or frequency) given (a) the research procedures that are described in the protocol-related documents, such as the IRB-approved research protocol and informed consent document; and (b) the characteristics of the subject population being studied;
2. Related or possibly related to a subject's participation in the research; and
3. Suggests that the research places subjects or others at a greater risk of harm (including physical, psychological, economic, or social harm) related to the research than was previously known or recognized.

An unanticipated problem may be an SAE and meet the reporting requirements of an SAE, or a UP may not manifest any criteria of an SAE and would therefore require reporting to the IRBs only, as per IRB requirements. All UPs occurring at any time during the 2-year treatment and additional year of follow-up will be reported.

8.4.3 Procedures to be Followed in the Event of Abnormal Laboratory Test Values or Abnormal Clinical Findings

Laboratory tests will not be performed in this study. If a dental emergency is found in a study child (e.g., a dental abscess), the child will be referred to the Head Start teacher, who has procedures in place for managing medical emergencies.

8.5 Reporting Procedures

8.5.1 Regulatory Reporting for Studies Conducted Under NIDCR-Sponsored IND

This study will not be conducted under an IND.

8.5.2 Regulatory Reporting for Studies Not Conducted Under NIDCR-Sponsored IND

All SAEs and UPs will be reported by the field staff to the study PI within 24 hours of receipt of the information in the field. The study PI will report all SAEs to NIDCR via the CROMS contractor, within 72 hours of receipt of information about the SAE. The CROMS contractor will notify the DCC.

All SAE forms and UP forms should be sent to:

Safety Fax Line: [contact] or [contact], or

Product Safety Email: [contact]

For information regarding SAEs, sites can contact the SAE Hotline for guidance:

Safety Hot Line: [contact] or [contact]

Unanticipated problems must be reported to the appropriate IRB per their requirements.

All medically attended events, SAEs and UPs will also be reported in each annual statistical progress report that is sent to the DSMB.

8.5.3 Other Adverse Events (if applicable)

Adverse events as defined in Section 8.4.1 of protocol occurring during the 3-10 days after each FV application will be recorded on the appropriate case report form and followed to resolution as noted in Section 8.6.

8.5.4 Reporting of Pregnancy

Not applicable

8.6 Type and Duration of Follow-up of Subjects after Adverse Events

Children who have a medically attended AE as defined in Sections 8.4.1-8.4.2 of the protocol will be followed weekly by the PI and/or study dentist until the AE resolves or stabilizes. This might include visits to the HSC or home visits by study staff. If the AE does not resolve within one month, the child will be referred to their usual medical or dental care provider as appropriate. If the need is/becomes urgent, immediate referral will be made.

8.7 Halting Rules

The frequency of AEs meeting criteria defined in protocol Section 8.4.1 in this study is expected to be very small. If the number of SAEs is large, or of a particular type, NIDCR and the Data and Safety Monitoring Board may consider temporarily suspending enrollment and/or the FV interventions until a safety review is convened. The objective of the safety review would be to make a decision on whether the study should continue per protocol, proceed with caution, be further investigated, be discontinued, or be modified and then continued.

8.8 Safety Oversight

NIDCR has appointed a Data and Safety Monitoring Board, which will review data from all of the studies in the ECC consortium. The conduct of the DSMB and rules regarding how often the Board will meet have been described in the DSMB Charter for the study.

9 CLINICAL MONITORING

9.1 Site Monitoring Plan

Site monitoring will be conducted to ensure that human subject protection, study procedures, study intervention administration, and data collection processes are of high quality and meet sponsor, GCP/ICH, and regulatory guidelines, and that the study is conducted in accordance with the protocol and sponsor SOPs. NIDCR, the sponsoring agency, or its designee will develop a site monitoring plan and conduct site monitoring visits as described in the site monitoring plan.

Site visits will be made at standard intervals as defined by NIDCR and may be made more frequently as directed by NIDCR. Monitoring visits will include, but are not limited to, review of regulatory files, accountability records, case report forms, informed consent forms, medical and laboratory reports, and protocol compliance. Study monitors will meet with investigators to discuss any problems and actions to be taken and document visit findings and discussions.

A separate monitoring plan document will be developed by the DSMB and the sponsor to describe who will conduct the monitoring, at what frequency monitoring will be done, and what level of detail monitoring will be conducted.

10 STATISTICAL CONSIDERATIONS

10.1 Study Hypotheses

The hypothesis of this study is that intensive intervention of specially trained COHS delivering fluoride varnish 4x a year and ongoing oral health promotion activities for 2 years to preschool children and families through Navajo Nation Head Start centers (Group 1) vs. the delivery of usual care (Group 2) will reduce the decayed missing and filled tooth surfaces increment in the Group 1 children when compared to the Group 2 children, and show improved parent/caregiver dental knowledge, attitudes, and behaviors. The dmfs measure is the primary outcome of the study on which sample size will be based.

10.2 Sample Size Considerations

Sample size is based upon the following assumptions:

1. The primary outcome measure is dmfs, measured at baseline and annually for three years after the beginning of the intervention when the HS children ages 3-5 at enrollment (or possibly 6, depending on the timing of enrollment) will be ages 6-8 (or possibly 9).
2. The test statistic used is the t-test for 2 independent samples, with an inflation factor for the cluster randomized design.^{29, 30}
3. The null hypothesis is no difference in the mean dmfs between the 2 randomized groups 2 years and 3 years after the beginning of the intervention when the children are 5-7 6-8 (or possibly 9) years old. The alternative hypothesis is that there is a difference.
4. Type I error rate will be set at 0.05
5. Type II error rate will be set at 0.20 (Power = 0.80)
6. From the 1999 IHS oral health survey ⁵, the average dmfs for AI children ages 5-7 was 18.55. It was also observed that Navajo children tended to have dmfs measures about 30% higher than the national average for all AI children. Therefore, it was assumed that the average dmfs for Navajo children ages 5-7 will be about 24 under conditions of usual care, with a standard deviation of about 24. We also assumed a 40% reduction in this average dmfs measure for group 1.
7. Based on the experience of other studies the Centers for American Indian and Alaska Native Health have conducted with AI communities, a 70% retention rate was assumed.

8. If subjects drop out of the study due to adverse effects or other reasons, we will ask them to continue in the follow-up even if treatment is discontinued, so that we can perform an “intention to treat” analysis. The “intention to treat” analysis will be the primary analysis of the study.
9. We also assumed an average HS class size of about 20 children and an intraclass correlation of about 0.045, considered to be an appropriate intraclass correlation.³¹

On the basis of the assumptions above, we calculate a need to randomize 52 HSC classrooms, or about 26 HSC classrooms in group 1 and 26 HSC classrooms in group 2. This means that we will need to enroll about 1040 children, or 520 children in group 1 and 520 children in group 2. Sample size calculations are shown in the table in *Appendix B*.

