5.3 Treatment Assignment Procedures

5.3.1 Randomization Procedures

A list of Navajo HSCs and the population sizes will be provided to the University of Colorado Center for Native Oral Health Research (CNOHR) by the Navajo Nation Head Start Program. The HSCs will be stratified by number of HS classes (1 vs. 2-3) and by Navajo

agency (there are 5 agencies), and then the randomization of the HSCs into intervention vs. control will be done within those strata. This will be done to ensure approximately equal sample sizes in the intervention and control groups, and approximately an equal number of intervention and control participants within each Navajo agency. A program will be developed to do the randomization within each stratum. Random numbers will be generated, and if the random number ends with the digit 0-4, the HSC will be assigned to the control arm and if the random number ends with the digit 5-9, the HSC will be assigned to the intervention arm.

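### Section 10.2's own inputs give 260 children per group, not 520; the stated 80% power matches neither that N with classes of 20 nor the dmfs increment under test, and the randomised unit is inconsistent

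*Combined protocol and SAP*

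**What the plan says.** **Effect and target.** Section 10.2 says "it was assumed that the average dmfs for Navajo children ages 5-7 will be about 24 under conditions of usual care", with an SD also of about 24, and then "We also assumed a 40% reduction in this average dmfs measure for group 1". Its test is on level: "The null hypothesis is no difference in the mean dmfs between the 2 randomized groups", at 2 and 3 years. Sections 2.2 and 10.1 put the hypothesis on the dmfs increment, and Sections 4 and 10.4 put the primary outcome on change from baseline. Section 3.2.1 and the last sentence of Section 10.1 call the outcome simply dmfs.

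**Sample size.** Section 10.2 sets Type I error 0.05, power 0.80 and retention 70%, and adds: "We also assumed an average HS class size of about 20 children and an intraclass correlation of about 0.045". From these, "we calculate a need to randomize 52 HSC classrooms, or about 26 HSC classrooms in group 1 and 26 HSC classrooms in group 2", and "we will need to enroll about 1040 children, or 520 children in group 1 and 520 children in group 2". It refers to a table in Appendix B, which the available text lists by title only.

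**Randomised unit.** Sections 4 and 10.2 assign classrooms. The Protocol Summary and Section 5.1 randomise centers (HSCs), as does Section 5.3.1: "The HSCs will be stratified by number of HS classes (1 vs. 2-3"), and "the randomization of the HSCs into intervention vs. control will be done within those strata". Section 10.4 treats the HSC as the cluster in the mixed model.

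**The concern.** Three parts of the sizing do not fit together.

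1. The sample size is presented as following from the listed assumptions, but it does not.
2. The design effect uses the size of one class, while the operative randomisation procedure allocates centers holding up to three classes.
3. The 40% reduction is taken from a total that includes disease already present at baseline, while the claim under test concerns disease that accrues afterwards.

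At stake is what the 80% figure means. As written, it describes neither the power of 1,040 children for 9.6 surfaces with classes of 20, nor the power for a 40% cut in the increment. Section 10.3 also says that the sample size will be adjusted once interim-analysis policy is set, and an adjustment needs a starting calculation that can be reproduced.

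**Working it through.** **Inputs (Section 10.2).** Control mean 24, SD 24, reduction 40%, alpha 0.05, power 0.80, ICC 0.045, class size 20, retention 0.70. The test is taken as two-sided because the alternative is non-directional. The mean can be reproduced: 18.55 × 1.30 = 24.1.

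**Step 1: N from the stated inputs.**
- Difference = 0.40 × 24 = 9.6 surfaces, or 0.40 SD.
- Before clustering: 2 × (1.960 + 0.842)² × (24/9.6)² = 98.1 per group.
- Design effect: 1 + (20 − 1) × 0.045 = 1.855.
- Enrolled: 98.1 × 1.855 / 0.70 = 260.0 per group, or 13 classrooms of 20.

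The plan states 520 per group. Variants do not reach it: the exact t-test gives 265, 90% power 348, alpha 0.025 gives 315, and cluster-level degrees of freedom at most about 314.

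**Step 2: what would give 520.** Each of these fits:
- A total of 2 × 260.0 = 520 taken as a per-group figure.
- A change-score SD of 24 × √2 = 33.9 (zero correlation between baseline and follow-up), which doubles the variance: 2 × 260.0 = 520.
- Clusters of about 61: (364/98.1 − 1)/0.045 + 1 = 61.2, where 364 = 520 × 0.70.

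**Step 3: power for 9.6 surfaces at 520 enrolled (364 retained) per group.** Effective n = 364 / design effect. Power = Φ(0.40 × √(effective n / 2) − 1.960). The cluster-df column uses a noncentral t with 2 × 520/m − 2 degrees of freedom, where m is cluster size.

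| Mean cluster size | Design effect | N needed per group | Effective n | Power | Power, cluster df | Detectable difference (80%) |
|---|---|---|---|---|---|---|
| 20 | 1.855 | 260 | 196.2 | 98% | 97% | 6.8 |
| 40 | 2.755 | 386 | 132.1 | 90% | 88% | 8.3 |
| 60 | 3.655 | 512 | 99.6 | 81% | 75% | 9.5 |

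Sizes 40 and 60 stand for centers with two or three classes of 20.

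Unequal sizes lower power further. For an assumed half-and-half mix of clusters of 20 and 60, the mean is 40 and the coefficient of variation 0.5. The design effect is 1 + (1.25 × 40 − 1) × 0.045 = 3.205. The N needed is 98.1 × 3.205 / 0.70 = 449, and power at 520 is 85%, against 386 and 90% for equal clusters of 40.

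**Step 4: the increment scale.** Randomisation makes the expected between-group difference the same for level and for increment. The relative size is not the same: 9.6/10 = 96%, 9.6/15 = 64% and 9.6/20 = 48% of increments of 10, 15 and 20, all assumed. The two means in the text, 19.0 at ages 2–5 (Section 2.1) and 24 at ages 5–7, differ by 5.0.

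Power at 520 per group for a 40% cut in the increment, with the increment and SD assumed and ICC 0.045 assumed to hold for change:

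| Increment | Cluster size | SD 8 | SD 12 | SD 16 | SD 24 |
|---|---|---|---|---|---|
| 5 | 20 | 70% | 38% | 24% | 13% |
| 5 | 40 | 53% | 27% | 17% | 10% |
| 10 | 20 | >99% | 91% | 70% | 38% |
| 10 | 40 | 98% | 77% | 53% | 27% |
| 15 | 20 | >99% | >99% | 96% | 70% |
| 20 | 20 | >99% | >99% | >99% | 91% |

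SD 24 is not a ceiling. If the SD is 24 at both visits, the change SD is 24 × √(2(1 − r)), which is 28.4 at an assumed correlation r = 0.3 and 10.7 at r = 0.9.

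**The case against.** **Sizing on level is sound.** Section 10.1 openly bases the sample size on dmfs, and Section 10.4 treats baseline as a covariate; with that adjustment, level and change give the same treatment estimate. This stands. The fault is not the choice of level. It is that the 40% is applied to a total that includes baseline disease, and that no increment or relevant SD is given.

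**Appendix B may explain 520, perhaps by a conservative change-score variance.** It may. A reader might infer from the exact factor of two that a total was misread as a per-group figure, but the documents do not support that over the other routes. Nor do they show that three-class centers explain it: if the design effect counts retained children only, clusters of 60 need 399, not 512. What stands is that Section 10.2's listed inputs do not yield its N. An appendix table would not reconcile Section 4 with Section 5.3.1 either.

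**The excess is conservative.** A reader might infer that the trial is twice as large as it needs to be. That holds only for 9.6 surfaces with clusters of 20. At clusters of 60 with cluster-level degrees of freedom, power is 75%.

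**The increment is unknown.** This stands too. A reader might set 9.6 against the gap of 5.0 and infer an impossible effect (192%). The two means are cross-sectional, come from different sources and overlap in age, and neither is stated to use the trial's criteria, which count non-cavitated lesions (Section 8.1). The gap is only indicative, and larger increments cannot be excluded.

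**A null result would be read from its confidence interval.** True, and neither conduct nor the estimator is affected. The point concerns the stated justification of the sample size.

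**Conclusion.** The concern holds as an error in the stated sample-size justification. With clusters of 20, Section 10.2's inputs give 260 per group, exactly half the stated 520, and power for 9.6 surfaces at 520 is about 98%, not 80%. If centers are the unit and average 40 to 60 children, power is about 90% to 81% (88% to 75% with cluster-level degrees of freedom), and lower at a given mean when sizes vary. These figures rest on ICC 0.045, SD 24, 70% retention and a design effect on enrolled children; counting retained children only gives 99%, 95% and 89% at cluster sizes 20, 40 and 60 (normal approximation).

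Power for a 40% cut in the increment cannot be computed from the documents and may lie well below or well above 80%. A reader might infer that the trial is underpowered for its hypothesis; the documents do not establish that. The arithmetic and the inconsistency of unit are certain. The cause of the doubling is not.

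**What to change.** With no change to enrolment:

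- **Sample size.** In Section 10.2 and Appendix B, correct or explain the 520 children and 26 classrooms per group. Either name the input that yields them or state that N exceeds the 80% requirement.
- **Randomised unit.** Use one unit throughout the Protocol Summary and Sections 4, 5.1, 5.3.1, 10.2 and 10.4. Compute the design effect for that unit from both the mean and the coefficient of variation of cluster size, and use cluster-level degrees of freedom.
- **Power.** Replace the 80% claim for a 40% cut in total dmfs with power and detectable difference for the existing 1,040 children at 70% retention, on the increment or baseline-adjusted scale. Give a range of usual-care increments and SDs that extends both below and above the expected values, with a source for each.

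The cost is text and table changes, and the team must commit to an increment, an SD and a cluster-size distribution. The downside is that the restated power may read below 80%.

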10.3 Planned Interim Analyses (if applicable)

Planned interim analyses will be established by the Data and Safety Monitoring Board appointed by NIDCR. Our planned sample size will be adjusted after the DSMB decides on their policy with regard to interim analyses.

10.3.1 Safety Review

SAEs will be reported to NIDCR Medical Monitor by the CROMS contractor within 24 hours of their receipt by the contractor. If the number, frequency, or character of the SAEs or UPs is unexpected, the investigator, NIDCR and/or the DSMB can call for a safety review (see section 8.7). AEs will be reported to the DSMB routinely in the semi-annual statistical progress report.

10.3.2 Immunogenicity or Efficacy Review

Not applicable.

10.4 Final Analysis Plan

The primary outcome measure will be the difference between groups 1 and 2 on the changes in mean dmfs between baseline and 2-year and 3-year follow-up. Descriptive statistics will be examined first to yield important information about the most appropriate analysis strategies. If the change scores for dmfs are not normally distributed, a log transformation can be made, or a non-parametric test can be used. Longitudinal methods of analysis will be used to examine these repeated, correlated observations within subjects over time.^{32, 33} Other models such as negative binomial regression, mixture models such as ZIP and ZINB will be considered.

Exploratory analyses will first be done to evaluate the trends in the data to determine the most appropriate mean and covariance structures for the data. Graphical displays will be used to assess the mean structure for modeling fixed effects, including scatter plots of the response variable versus time, plots of individual subject profiles, plots of mean profiles, and smooth curve fits to the data. Simple plots of individual subject profiles (dmfs over time) can be very revealing and show whether there is heteroscedasticity in the data (fanning of the curves with time).

Linear mixed models will be used because they can incorporate both fixed and random (subject-specific) effects and permit different covariance structures. A typical example (“random regression”) allows each subject an individual time trend, and treatment effects may cause differences in slope over time. The within-subjects autocorrelation is assumed to be due to these individual trends, on top of which is superimposed independent measurement errors. When analyzing randomized trials, it is assumed that the responses are the values that occur after randomization, because they are influenced by treatment. Thus, it is customary in such trials to consider the baseline value as a covariate, rather than as a response variable. The randomization of subjects in groups or clusters (i.e., HSCs) can also be accounted for in the mixed model with a random effect for group.

Two important considerations in fitting mixed models are determining covariance and mean structures for the data. We will first define the covariance structure; many forms are available, depending on the correlations in the data. Little, et al.,³⁴ provide a useful article on modeling the covariance structure for longitudinal data by using the MIXED procedure in SAS software. Once a suitable covariance structure has been determined, an appropriate mean structure can be determined.

Missing or incomplete data are a common problem in randomized clinical trials where the outcome is measured longitudinally. Here, exploratory analyses will be done first to determine if the missing observations are missing completely at random (MCAR), missing at random (MAR), or missing not at random (MNAR) and whether multiple imputation should be done, or modeling of the non-response. Complete case analysis will be the primary analysis,

since available data analysis with mixed models only assumes MAR (Molenberghs). As a secondary analysis multiple imputation or modeling of the non-response mechanism will be done to include those cases without complete data.

The secondary outcomes will include caries patterns, cost analyses and the array of information representing knowledge, attitudes, and behaviors of parents that may serve as mediating and moderating variables. Caries patterns will be analyzed by looking at the different dmfs components and the specific teeth involved.

Cost-effectiveness analysis is used to compare costs of alternative interventions for a similar health outcome. Results are presented as a cost-effectiveness (or CE) ratio of the intervention net cost (intervention costs minus savings) per health outcome such as improvement in quality-adjusted life years (QOL). For this proposal, intervention cost and net cost estimates will be used to construct cost indicators such as the cost/net cost per child served and, if the program is found to be effective, the cost/net cost per unit decrease in caries. Such indicators are sometimes referred to as preliminary CE ratios for 2 reasons. First, the ratios measure the cost for a process-outcome or a health-outcome such as caries rather than QOL. Second, we will estimate only short-term net intervention costs, not long-term costs that may result with improvements in oral health behaviors and practices overtime.

We will document all costs associated with the intervention from two perspectives, that of the provider and that of society, which includes both provider and participant direct and indirect intervention costs. Costs include direct dental and medical costs; other direct costs (e.g., costs for travel to obtain services), and indirect costs (e.g., costs associated with patient time spent for a dental visit, time spent off work). Intervention costs from the provider perspective include direct costs for all stages of program implementation (adapting the intervention for use in this population, service implementation, and service provision), excluding research costs. They include costs of any additional dental services study participants incurred as a result of the intervention (e.g., utilization of preventive dental services). Participant intervention costs (e.g., time and travel costs) will also be accounted for. We will assess intervention savings by estimating averted treatment costs due to a reduction in ECC using parent-reported data on children's use of dental and medical services for oral health problems, time spent obtaining services, and travel costs.³⁵⁻³⁸ Standardized price data will be used to value service utilization, non-clinical intervention costs, travel costs, and time costs.

Provider and participant intervention cost will be summed to calculate total intervention costs. Short-term net costs will be obtained by subtracting intervention savings from the total intervention costs. We will compare the intervention costs and net costs incurred in groups 1 and 2, and preliminary cost-effectiveness ratios (e.g., the cost per participant and cost per averted cary). We will examine the influence of demographic and clinical characteristics on the cost findings. Finally, we will conduct sensitivity analyses to evaluate the inherent uncertainty of

assumptions concerning costs on the findings. The sensitivity analyses will include univariate analyses and second-order Monte Carlo sensitivity analyses.³⁹

In a series of secondary analyses, hierarchical models will be constructed wherein potential mediators and moderators such as parental knowledge, attitudes and behaviors, are added to the primary outcome model to assess the degree to which these factors explain the relationship between intervention conditions and dmfs changes. For instance, a sequence might be as follows: 1) intervention condition; 2) intervention condition + sociodemographics; and 3) intervention condition + sociodemographics + mediators. Using the approach recommended by Hosmer and Lemeshow,⁴⁰ we will first assess the bivariable relationships of each variable with dmfs. Only those variables with a bivariable relationship at $p \leq 0.25$ will be included in these final models.

The potential of specific variables to have moderating effects will be assessed through the use of interaction terms; for instance, we might find that those with high levels of chronic stress in their lives are less likely to incorporate the important health behaviors that the COHS encourage into their everyday lives.

